#### **8.4.7 Achenbach CBCL**

The Achenbach CBCL is a widely used validated questionnaire to evaluate a child’s competencies and behavioral/emotional problems. Behavioral problems will be scored by the parent(s)/legal representative(s). Depending on the subject’s age, 2 versions of the CBCL will be used. The CBCL/1½-5 checklist is intended for use in children 18 months to 5 years and 11 months of age. For subjects ≥6 years to ≤17 years of age, the CBCL/6-18 version will be used.

The Achenbach CBCL will be completed according to the tabular schedule of study procedures, [Section 16.1](#).

In both questionnaires, the occurrence of certain problems and behaviors (in the past 2 months for the CBCL/1½-5 version and in the past 6 months for the CBCL/6-18 version) will be scored on the following scale:

- 0=not true (as far as known)
- 1=somewhat or sometimes true
- 2=very true or often true

Syndrome scores will be calculated from these questions, which will in turn be summarized by 2 composite scores. Additionally, for each syndrome and composite scores, categorizations based on a normative sample will be used to evaluate normal, borderline, or clinically relevant behavior.

In addition, the Achenbach CBCL/6-18 includes ratings related to performance in school, activities in leisure time, and special interests.

#### **8.4.8 Bayley Scales of Infant and Toddler Development, Third Edition**

The Bayley-III scales are recognized internationally as one of the most comprehensive developmental assessment instruments (Sattler and Hoge, 2006) used to examine the major facets of a young child’s development (Bayley, 2006). The Bayley Scales of Infant and Toddler Development, Third Edition (Bayley-III) are a standardized individually administered adaptive assessment that measures the developmental functioning of infants and young children from 1 month to 42 months of age (Bayley, 2006). The Bayley-III scales measure cognitive, language, motor, social-emotional, and adaptive development and are a revision of the predecessor, the Bayley Scales of Infant Development, Second Edition (BSID-II) (Bayley, 1993). The Bayley-III

scales are a technically sound instrument, with strong internal consistency, as well as test-retest stability. The Bayley-III scales are validated only in English.

This scale is validated as a tool for assessment of neurological development in young children and is therefore considered appropriate for SP848.

The Bayley-III scales are an individually administered adaptive assessment that presents children with situations and tasks designed to produce an observable set of behavioral responses. They consist of a cognitive scale, a language composite scale with receptive and expressive language subscales, and a motor composite scale with fine and gross motor subscales to be completed by the Investigator or designee, and of a social-emotional scale, comprising social emotional competence, and sensory processing, and an adaptive behavior scale, which assesses the attainment of skills necessary for the development of independence, to be completed by the child's parent or caregiver.

The completion of the Bayley-III scales will require approximately 50 minutes for children who are 12 months old or younger and 90 minutes for children aged 13 months and older.

The Bayley-III scales will be completed according to the tabular schedule of study procedures, [Section 16.1](#).

#### **8.4.9 Palatability and ease of use questionnaire for LCM**

UCB BIOSCIENCES has created a palatability and ease of use questionnaire to collect data from the subject or caregiver regarding different aspects of LCM and its administration. The questionnaire will assess the subject or caregiver's response regarding the formulation of LCM the subject is receiving for palatability items (eg, taste, smell, ability to swallow, aftertaste), mode of administration, and administration device as applicable.

The questionnaire will be completed according to the tabular schedule of study procedures, [Section 16.1](#).

#### **8.4.10 Behavior Rating Inventory of Executive Function**

The BRIEF-P and the BRIEF are validated tools that will be used for the evaluation of subjects  $\geq 2$  years to  $<5$  years of age and  $\geq 5$  years of age, respectively. The BRIEF-P/BRIEF will be administered according to the tabular schedule of study procedures, [Section 16.1](#).

The BRIEF-P and BRIEF include rating forms used by parents to assess subjects' executive functioning. Executive functions broadly encompass a set of cognitive skills that are responsible for the planning, initiation, sequencing, and monitoring of complex goal-directed behavior.

The BRIEF-P rating form consists of items that measure various aspects of executive functioning: Inhibit, Shift, Emotional Control, Working Memory, and Plan/Organize. The clinical scales form 3 broad indexes (Inhibitory Self-Control, Flexibility, and Emergent Metacognition) and 1 composite score (Global Executive Composite).

The BRIEF rating form consists of items that measure various aspects of executive functioning: Inhibit, Shift, Emotional Control, Initiate, Working Memory, Plan/Organize, Organization of materials, and Monitor. These clinical scales form 2 broader Indexes: Behavioral Regulation (3 scales) and Metacognition (5 scales), as well as a Global Executive Composite score.

Both the BRIEF-P and the BRIEF include validity scales to measure negativity and inconsistency of responses.

## **9 MANUFACTURING, HANDLING, AND ACCOUNTABILITY OF STUDY MEDICATION**

### **9.1 Manufacturing, packaging, and labeling**

Lacosamide is manufactured, packaged, and labeled according to Good Manufacturing Practice guidelines and applicable laws and regulations. It is suitably packaged, in such a way as to protect the product from deterioration during transport and storage.

#### **Description of packaging:**

Lacosamide oral solution (syrup) will be packaged in 200mL amber PET bottles with a white, child-proof, polypropylene screw cap. Different volumes of LCM syrup will be taken to obtain the appropriate dose.

Lacosamide tablets will be packaged in high-density polyethylene bottles with a child-proof, polypropylene screw cap.

#### **Contents of the labels:**

The labels for LCM will include the following information (not all information will appear on all labels):

- Sponsor name, address, and telephone number
- Statement “Caution: New drug – Limited by federal law to investigational use”
- Statement “For clinical trial use only”
- Study number
- Kit number
- Pharmaceutical dosage form
- Name of drug
- Route of administration
- Directions for use
- Date bottle opened
- Do not use after (date)
- Strength per unit
- Quantity of dosage units
- Batch number
- Statement “Keep out of reach of children”
- Storage conditions
- Expiry date

- Subject number
- Visit number
- Date dispensed
- Name of investigator and telephone number
- Statement “Return all empty, partially used, and unused product”
- Statement “Class scheduling as a controlled substance”

## **9.2 Supply, handling, and storage**

Lacosamide (oral solution [syrup] and tablet) is stable at room temperature and is to be stored at temperatures not exceeding 25.4°C (77.7°F) or below 14.5°C (58.1°F). Lacosamide should not be frozen or refrigerated.

The investigator (or designee) is responsible for safe and proper storage of LCM at the site. Lacosamide stored by the investigator is to be kept in a secured area with limited access according to the storage conditions mentioned on the label.

Appropriate storage conditions must be ensured either by controlling the temperature and by completion of a temperature log in accordance with local requirements on a regular basis, showing minimum and maximum temperatures reached over the time interval.

In case an out-of-range temperature is noted, it must be immediately reported as per instructions contained in the IMP Handling Manual.

The investigator (or designee) will instruct the subject to store the IMP following the instructions on the label.

## **9.3 Drug accountability procedures**

A Drug Accountability form will be used to record LCM dispensing and return information on a by-subject basis and will serve as source documentation during the course of the study. Details of any LCM lost, damaged (due to breakage or wastage), not used, partially used, disposed of at the study site, or returned to the sponsor or designee must also be recorded on the appropriate forms. All supplies and pharmacy documentation must be made available throughout the study for UCB (or designee) to review.

The investigator (or designee) is responsible for retaining all used, unused, and partially used containers of LCM until returned or destroyed by a UCB representative.

The investigator may assign some of the investigator's duties for drug accountability at the study site to an appropriate pharmacist/designee.

The investigator must ensure that LCM is used only in accordance with the protocol.

Periodically, and/or after completion of the clinical phase of the study, all used (including empty containers)/partially used, unused, damaged, and/or expired LCM must be reconciled and either destroyed at the site according to local laws, regulations, and UCB SOPs or returned to UCB (or designee). Investigational medicinal product intended for the study cannot be used for any other purpose than that described in this protocol.

## **9.4 Retrieval/recall of study medication**

Lacosamide being returned following study completion or due to product expiration or defect should be returned to UCB BIOSCIENCES or designee for final inventory using the provided forms. UCB BIOSCIENCES or designee will oversee destruction of returned drug after the clinical study report is completed.

## **9.5 Alternative study treatment supply due to COVID-19 pandemic**

When a subject can no longer return to the study site due to general circumstances but will continue in the study, the following methods may be used to provide study treatment:

- Site to subject: In instances where site staff can ship study treatment dispensed from the site pharmacy supply directly to the subject.
- Depot to subject: In instances where it is not possible for the site staff to access study treatment in the site pharmacy and/or ship study treatment dispensed from the site pharmacy supply directly to the subject.

# **10 DATA QUALITY CONTROL AND QUALITY ASSURANCE**

## **10.1 Site qualification**

A site visit will be performed by UCB BIOSCIENCES or designee to discuss the protocol, to ensure the availability of appropriate study personnel, adequate resources, and to assess their ability to properly conduct the study according to International Council for Harmonisation-Good Clinical Practice (ICH-GCP) guidelines and local requirements. These procedures do not need to be repeated for this extension study (if a site needs to be added to SP848 that did not participate in SP847, an assessment will be made to determine whether a site visit is required).

## **10.2 Monitoring**

UCB BIOSCIENCES or designee will monitor the study to meet the Sponsor's monitoring standard operating procedures (SOPs), ICH-GCP guideline, and applicable regulatory requirements and to ensure that study initiation, conduct, and closure are adequate. Monitoring of the study may be delegated by UCB BIOSCIENCES to a CRO or a contract monitor.

The investigator and his/her staff will be expected to cooperate with UCB BIOSCIENCES personnel or agents of UCB BIOSCIENCES and to be available during the monitoring visits to answer questions sufficiently and to provide any missing information.

The investigator(s)/institution(s) will permit direct access to source data/documents for study-related monitoring, audits, IRB/IEC review, and regulatory inspections.

### **10.2.1 Definition of source data**

All source documents must be accurate, legible, clear, unambiguous, permanent, and capable of being audited. They should be made using some permanent form of recording (ink, typing, printing, optical disc). They should not be obscured by correcting fluid or have temporary attachments (such as removable self-stick notes). Photocopies of CRF forms are not considered acceptable source documents.

Source documents are original records in which raw data are first recorded. These may include hospital/clinic/physician records, charts, diaries, x-rays, laboratory results, printouts, pharmacy

records, care records, ECG or other printouts, completed scales, or Quality of Life Questionnaires, for example. Source documents should be kept in a secure, limited access area.

Source documents that are computer generated and stored electronically must be printed for review by the monitor (eg, ECG reports). Once printed, these copies should be signed and dated by the investigator and become a permanent part of the subject's source documents. The investigator will authorize the monitor to compare the content of the printout and the data stored in the computer to ensure all data are consistent.

Electronic data records, such as Holter monitor records or EEG records, must be saved and stored as instructed by UCB BIOSCIENCES (or designee).

### **10.2.2      Source data verification**

Source data verification ensures accuracy and credibility of the data obtained. During monitoring visits, reported data are reviewed with regard to being accurate, complete, and verifiable from source documents (eg, subject files, recordings from automated instruments, tracings [ECG], x-ray films, laboratory notes). All data reported on the eCRF should be supported by source documents.

### **10.3        Auditing**

The investigator will permit study-related audits mandated by UCB, and inspections by domestic or foreign regulatory authorities.

The main purposes of an audit or inspection are to confirm that the rights and well-being of the subjects enrolled have been protected, that enrolled subjects (ie, signing consent and undergoing study procedures) are appropriate for the study, and that all data relevant for the evaluation of the IMP have been processed and reported in compliance with the planned arrangements, the protocol, investigational site, and IRB/IEC SOPs, ICH GCP, and applicable regulatory requirements.

The investigator will provide direct access to all study documents, source records, and source data. If an inspection by a regulatory authority is announced, the investigator will immediately inform UCB (or designee).

## **11            DATA HANDLING AND RECORD KEEPING**

The parent/legal guardian's consent, subject's assent, and enrollment in the study must be recorded in the subject's medical record. These data should identify the study and document the dates of the subject's participation.

### **11.1        Case Report form completion**

This study is performed using remote data capture (RDC); the investigator is responsible for prompt reporting of accurate, complete, and legible data in the eCRFs and in all required reports. Any change or correction to the eCRF after saving must be accompanied by a reason for the change. Corrections made after the investigator's review and approval (by means of a password/electronic signature) will be reapproved by the investigator. The investigator should maintain a list of personnel authorized to enter data into the eCRF. Detailed instructions will be provided in the eCRF Completion Guidelines.

## 11.2 Database entry and reconciliation

Electronic Case Report forms/external electronic data will be entered/loaded into a validated electronic database using a clinical data management system (CDMS). Computerized data cleaning checks will be used in addition to manual review to check for discrepancies and to ensure consistency of the data. This study is performed using RDC; the data are entered into the eCRFs once and are subsequently verified. An electronic audit trail system will be maintained within the CDMS to track all data changes in the database once the data have been saved initially into the system or electronically loaded. Regular backups of the electronic data will be performed.

## 11.3 Subject Screening and Enrollment log/Subject Identification Code list

The subject's screening and enrollment will be recorded in the Subject Screening and Enrollment log.

The investigator will keep a Subject Identification Code list. This list remains with the investigator and is used for unambiguous identification of each subject.

## 11.4 Archiving and data retention

The investigator will maintain adequate records for the study, including eCRFs, medical records, laboratory results, Informed Consent documents, drug dispensing and disposition records, safety reports, information regarding participants who discontinued, and other pertinent data.

All essential documents are to be retained by the investigator until at least 2 years after the last approval of a marketing application in an ICH region and until there are no pending or contemplated marketing applications in an ICH region, or at least 2 years have elapsed since the formal discontinuation of clinical development of the IMP. These documents should be retained for a longer period, however, if required by the applicable regulatory requirement(s) or by an agreement with UCB (CPMP/ICH/135/95, 2002 [Section 4.9.5]). The investigator will contact UCB for authorization prior to the destruction of any study records or in the event of accidental loss or destruction of any study records. The investigator will also notify UCB should he/she relocate or move the study-related files to a location other than that specified in the sponsor's trial master file.

## 11.5 Data management

Details regarding data management will be elaborated in the study-specific Data Management Manual.

## 12 STATISTICS

This study has an explorative, descriptive aim and does not intend to prove or disprove any statistical hypotheses. Hence, inferential statistical tests are not planned for the primary and secondary variables described below.

### 12.1 Description of statistical methods

Descriptive statistics will be used to provide an overview of the study results. For categorical parameters, these will consist of the number and percentage of subjects in each category. The

denominator for percentages will be based on the number of subjects appropriate for the purpose of analysis. For continuous parameters, descriptive statistics will include the number of subjects (n), mean, standard deviation (SD), median, minimum, and maximum.

Visit 1 of SP847 (or other primary study as applicable) or the Screening Visit of SP848 (for subjects who enter directly into SP848) will serve as Baseline values for safety and efficacy variables unless otherwise noted.

Further statistical methods are presented below, and will be described in more detail in the Statistical Analysis Plan.

### **12.1.1      Definition of analysis sets**

The Safety Set (SS), which is defined as all enrolled subjects who take at least 1 dose of LCM in this study. All safety analyses will be performed on the SS.

The Pharmacokinetic Per-Protocol Set (PK-PPS) will consist of all subjects from the SS having provided at least 1 measurable post-dose plasma sample (with recorded sampling time) on at least 1 visit with documented LCM intake times.

The Full Analysis Set (FAS) will be used for the analysis of seizure data and will consist of all subjects in the SS, who have at least 1 completed post-Baseline seizure diary.

### **12.1.2      Statistical analysis of safety variables**

#### **12.1.2.1      Primary safety variables**

The primary variables, for assessment of safety and tolerability, are the incidence of TEAEs and the incidence of SAEs.

##### **12.1.2.1.1      AEs**

Adverse events will be coded using the Medical Dictionary for Regulatory Activities (MedDRA®), and tabulated by system organ class and preferred term.

Treatment-emergent AEs will be defined as those events which started on or after the date of first SP848 LCM administration, or whose severity worsened on or after the date of first SP848 LCM administration. Adverse events occurring within 30 days after last dose of LCM will be considered treatment-emergent. The incidence of TEAEs will be presented by system organ class and preferred term. Serious AEs will also be tabulated and listed.

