## **4.2 Variables to be assessed**

### **4.2.1 Safety variables**

#### **4.2.1.1 Primary safety variables**

The primary safety variables are:

- Incidence of TEAEs
- Incidence of serious AEs (SAEs)
- Subject withdrawal from the study due to TEAEs

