## 4.3 Selection and withdrawal of subjects

### 4.3.1 Inclusion criteria

All subjects in SP848 must fulfill the following inclusion criteria:

1. A signed informed consent form has been obtained from the parent/legal guardian and assent has been obtained from the subject (when possible or as required according to local Institutional Review Boards [IRBs]/Independent Ethics Committees [IECs]).

4. Subject and caregiver (which may be a parent, legal guardian, or other delegated caregiver) are willing and able to comply with all study requirements, including maintaining a daily seizure diary.

**Subjects who have participated in SP847 or other LCM pediatric clinical studies in epilepsy must fulfill the following inclusion criteria:**

2. Subject has completed SP847 (or the subject discontinued SP847 due to a dose reduction or status epilepticus) for the treatment of uncontrolled partial-onset seizures, or subject has participated in other LCM pediatric clinical studies in epilepsy.
3. Subject is expected to benefit from participation, in the opinion of the investigator.

**Subjects who enroll directly into SP848 without previous participation in a LCM clinical study must fulfill the following inclusion criteria:**

5. Subject is male or female and  $\geq 4$  years to  $\leq 17$  years of age.
6. Subject has a diagnosis of epilepsy with partial-onset seizures.
  - The results of at least 1 prior electroencephalogram (EEG) AND 1 prior magnetic resonance imaging/computerized tomography scan should be consistent with the above diagnosis.
7. Subject has been observed to have uncontrolled partial-onset seizures after an adequate course of treatment (in the opinion of the investigator) with at least 2 AEDs (concurrently or sequentially).
8. Subject has been observed to have at least 2 countable seizures in the 4-week period prior to Screening.
  - In the case of simple partial seizures, only those with motor signs will be counted towards meeting the inclusion criteria (only partial seizures with a recognizable and countable manifestation).
9. Subject is on a stable dosage regimen of 1 to 3 AEDs. The daily dosage regimen of concomitant AED therapy must be kept constant for a period of at least 1 week prior to Screening. Vagal nerve stimulation is not counted as medical therapy; however, VNS settings must be kept constant for a period of at least 1 week prior to Screening.
10. Subject is an acceptable candidate for venipuncture.

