### **8.1.5 Rule for repetition of an adverse event**

An increase in the intensity of an AE should lead to the repetition of the AE being reported with:

- the outcome date of the first AE that is not related to the natural course of the disease being the same as the start date of the repeated AE, and the outcome of “worsening”,
- the AE verbatim term being the same for the first and repeated AE, so that the repeated AE can be easily identified as the worsening of the first one.

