- n Lacosamide for taper will be dispensed only for subjects who achieve a dose of LCM  $\geq 6\text{mg/kg/day}$  (oral solution [syrup]) or  $\geq 300\text{mg/day}$  (tablet). It is recommended that the LCM dose be tapered gradually in weekly decrements of  $4\text{mg/kg/day}$  (oral solution [syrup]) or  $200\text{mg/day}$  (tablet). A slower taper of  $2\text{mg/kg/day}$  (oral solution [syrup]) or  $100\text{mg/day}$  (tablet) is permitted, if medically necessary. In case of an emergency, a faster taper is permitted after discussion with the medical monitor, whenever possible.
- o As applicable.
- p For all subjects  $\geq 6$  years of age already enrolled, the “already enrolled” version should be completed at the next clinic visit, and the “since last visit” version should be completed thereafter.
- q The C-SSRS assessment should be completed if the Unscheduled Visit is due to an AE.
- r Ongoing AEs from the primary study will be followed, as well as recording of new AEs during the current study.

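### A rollover child withdrawn from SP848 for a carried-over adverse event that has not worsened is missed by the variable withdrawal due to TEAEs

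*Protocol*

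**What the plan says.** The TEAE definition in Section 12.1.2.1.1 has two limbs. The first is onset: "Treatment-emergent AEs will be defined as those events which started on or after the date of first SP848 LCM administration". The second is worsening: "or whose severity worsened on or after the date of first SP848 LCM administration". A further sentence closes the window: "Adverse events occurring within 30 days after last dose of LCM will be considered treatment-emergent".

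Section 4.2.1.1 lists three primary safety variables, the third being "Subject withdrawal from the study due to TEAEs". Section 12.1.2.1 gives a shorter list: "The primary variables, for assessment of safety and tolerability, are the incidence of TEAEs and the incidence of SAEs".

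For children coming from another LCM study, footnote r of Table 16-1 says "Ongoing AEs from the primary study will be followed, as well as recording of new AEs during the current study". Section 8.1.5 deals with worsening: "An increase in the intensity of an AE should lead to the repetition of the AE being reported with" a new start date, equal to the outcome date of the first record.

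**The concern.** Rollovers are already taking LCM when they receive their first SP848 dose, so for them the definition restarts the clock in the middle of treatment. For incidence, that separates new events from events already reported in the primary study. Withdrawal is different, because it happens in SP848 whenever the causal event began. A child who enters with an LCM-era adverse event, tolerates it for a time, and then leaves because it has not gone away is an SP848 withdrawal caused by an adverse event on LCM. The variable as worded does not count that child.

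The study's purpose is long-term safety and tolerability, and its data are meant for regulatory submissions. An event that wears a child down by lasting, without becoming more severe, is one that long exposure should reveal. The omission works in one direction only: it can lower the reported withdrawal figure and cannot raise it.

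**Working it through.** The plan gives no figure to reproduce: Section 12 describes a descriptive study without hypothesis tests. The check is to apply the definition case by case, ask whether the uncounted case can arise, and then see what can be said about size.

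**1. Applying the rule.** TEAE = (onset on or after first SP848 dose) OR (severity worsened on or after first SP848 dose).

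| Case | Onset limb | Worsening limb | TEAE | Withdrawal counted |
|---|---|---|---|---|
| New event in SP848 | yes | not needed | yes | yes |
| Ongoing at Visit 1, then worsens | no | yes | yes | yes |
| Ongoing at Visit 1, same severity | no | no | no | no |
| Direct enrollee, event starts in titration | yes | not needed | yes | yes |

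The second row is also secured by Section 8.1.5, which re-records the worsened event with a start date in SP848. Only the third row fails. The fourth row shows an asymmetry: direct enrollees take their first SP848 dose at the first Titration Visit (Section 5.2), so an event that begins in their titration and later forces withdrawal is counted. The same event beginning on LCM in SP847 is not, although Section 12.1.1 places both groups in one Safety Set.

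**2. Can the third row arise?**

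- Section 4.3.2, criterion 2, keeps out rollovers with an ongoing serious event and those meeting the primary study's withdrawal criteria, with stated exceptions. Other ongoing non-serious events are not a bar.
- Section 4.3.1, criterion 2, admits some children who stopped the primary study early: "Subject has completed SP847 (or the subject discontinued SP847 due to a dose reduction or status epilepticus".
- Table 16-1, footnote r, expects carried-over events and has them followed.
- Section 4.3.3, criterion 1, requires withdrawal for intolerable adverse events and does not limit this to treatment-emergent ones.

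So the case is possible under the protocol's own rules.

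**3. Does another passage repair it?** The 30-day sentence sets the end of the window and says nothing about onset before the first SP848 dose. Section 8.1.1 asks for events that are new, recurred or worsened after the initial visit, which again leaves out an unchanged one. Section 12.1 takes Visit 1 of the primary study as the default Baseline for rollovers' safety variables, but does not apply this to TEAEs. Nothing brings the third row back in.

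**4. Size.** The protocol gives neither the share of rollovers with an ongoing event at Visit 1 nor the share who later leave because of one, so no expected number can be computed. What follows from stated counts is the weight of each missed child, taking k missed withdrawals as an assumption from 1 to 10 and rate lost = k / N:

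- N = 400 (approximate upper total, Section 12.2): k = 1, 2, 5, 10 gives 0.25, 0.5, 1.25, 2.5 percentage points.
- N = 42 (approximate number eligible from SP847, Section 12.2): k = 1, 2, 5, 10 gives 2.4, 4.8, 11.9, 23.8 percentage points.

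The number of rollovers can be bracketed if all 400 places fill. Section 12.2 allows about 100 direct enrollees, 46 in Japan and 60 described as additional in China. It does not say whether the 46 fall within the 100. Direct enrollees are therefore 100 + 60 = 160 to 100 + 46 + 60 = 206, and rollovers 400 - 206 = 194 to 400 - 160 = 240.

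**The case against.** The strongest reply is that counting TEAEs from the first dose of the current study is an accepted convention for extensions: it keeps SP848 events apart from those already reported. That stands for TEAE incidence, which needs no change. It does not cover withdrawals, because the primary study recorded the event but the child left SP848.

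Second, the group is small. To be missed, a child must enter with a non-serious event, be judged likely to benefit, leave because of that same event, and have no worsening recorded. The dose may also be lowered along the way, including after a telephone contact. This stands and limits the weight of the point.

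Third, the information is not lost. Carried-over events are followed, and Section 4.3.3 requires the eCRF to give the primary reason for withdrawal. The SAP, which was not at hand, may tabulate such withdrawals. That is a fair mitigation, but the protocol itself fixes both the TEAE definition and the variable built on it, so a supplementary table would leave that variable as it is.

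Fourth, the variable's standing as primary is uncertain, since Section 12.1.2.1 does not name it. This is correct, and is itself a contradiction with Section 4.2.1.1 that needs resolving.

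**Conclusion.** The point holds in a narrow form. For rollovers, a non-serious event that began on LCM in the primary study, is ongoing at SP848 Visit 1 and does not worsen from the first SP848 dose is not a TEAE, and a later withdrawal for it is not counted under Section 4.2.1.1. The variable can therefore only understate adverse-event-related withdrawal in rollovers. The conclusion rests on the wording alone; its numerical effect depends on rates that the protocol does not give.

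Three stronger readings are not supported. A reader might infer that every carried-over event falls outside the TEAE definition, but the worsening limb and Section 8.1.5 bring worsened ones in. A reader might attach a percentage to the understatement, but that would require unsourced rates for ongoing events and for withdrawals due to them. A reader might conclude that TEAE incidence is also wrong, but restarting the clock for new-onset incidence in an extension is acceptable. The change is worth making because it is cheap and the variable may be reported as primary, not because a large bias has been shown.

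**What to change.** Leave the TEAE definition in Section 12.1.2.1.1 and the TEAE incidence tables unchanged. In Sections 4.2.1.1 and 12.1.2.1, define the withdrawal variable as withdrawal from SP848 due to any adverse event on LCM, and show two components separately: withdrawals due to TEAEs, and withdrawals due to events carried over from the primary study (onset on or after the first LCM dose there, ongoing at SP848 Visit 1, not worsened from the first SP848 dose). In the same edit, make the two sections agree on whether withdrawal is a primary safety variable.

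The cost is one derived flag and one extra table row. The events and the reasons for withdrawal are already collected. The flag does need onset dates and the date of first LCM dose from each primary study, so some linkage work is involved. The total withdrawal figure may become slightly less favourable; the TEAE component stays as now defined.
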